6.3 Enrollment Visit

During the enrollment process, the following baseline data will be collected for all patients.

Baseline Data (all patients)

- Patient demographics
- Arrhythmia history
- Cardiovascular history (including most recent LVEF)
- Cardiac medications
- NYHA class (CRT patients only)
- 12-lead ECG (most recent for CRT patients only)

Additional procedure related data will be collected specific to the procedure. Definitions for the beginning and ending of procedural steps are also provided.

CRT Group

- Devices implanted, i.e., leads and pulse generator
- MediGuide™ tools used at each step of the procedure if applicable
- MediGuide™ software version used if applicable
- Coronary venous anatomy
- Amount of fluoroscopy time and radiation dose in either $\text{cGray}\cdot\text{cm}^2$ or $\mu\text{Gray}\cdot\text{m}^2$ during the following steps in the procedure.
 - i. CS cannulation: From the moment the operator directs the technique to cannulate CS until the outer catheter is stable in CS
 - ii. LV lead placement: From the moment outer catheter is stable in LV until the suture sleeve for LV lead is tied down
 - iii. Any other steps that required the usage of fluoroscopy
- Electrical lead measurements for the RA, RV and LV leads
- Device session record

EP Group

- MediGuide™ tools used at each step of the procedure if applicable
- MediGuide™ software version used if applicable
- Mapping software used
- Ablation parameters
- Ablation site
- Amount of fluoroscopy time and radiation dose during the following steps in the procedure
 - i. Catheter insertion: Similar to CS cannulation for CRT implant
 - ii. Trans-septal puncture: From the moment of introducing trans-septal sheath until the sheath is stably paced in LA and the dilator is removed
 - iii. Geometry creation/Mapping: From the beginning of geometry creation until the complete creation of geometry including mapping as determined by an operator
 - iv. Ablation: From the beginning of ablation until the last attempt for ablation is made
 - v. Any other steps that required the usage of fluoroscopy

Additional Implant/Procedure Related Data (all patients)

- Total procedure: Skin to skin
- Total amount of fluoroscopy time and radiation dose
- Room time: From the moment the patient enters the operation room until the patient exits the operation room
- Number, experience and type of attending personnel
- Fluoroscopic views with orientations and angles
- Types of anesthesia used: conscious sedation vs. general
- Adverse events, if applicable

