4.4.2 Point of Enrollment

Subjects are considered enrolled in the study if the subject has provided written Patient Informed Consent and CRT implant or an EP procedure was attempted.

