6.2 Procedures

The clinical study will be conducted in accordance with the CIP. All parties participating in the conduct of the clinical study will be qualified by education, training, or experience to perform their tasks, and this training will be documented appropriately.

The clinical study will not commence until SJM receives written approval from the IRB/EC and relevant regulatory authorities and all required documents have been collected from the site(s).

Upon site activation, participating clinician’s previous experience in performing CRT or EP cases with or without utilizing MediGuide™ enabled tools will be collected via one-time survey.

Table 1: List of all study specific activities/procedures

	CRT Group at Enrollment	EP Group at Enrollment	Discharge
Baseline Demography	X	X	
Medical History	X	X	
Medications	X	X	
12 Lead ECG (most recent)	X		
Echo Measurements (including most recent LVEF)	X	X	
NYHA	X		
Device Session Record	X		
Fluoro Time and Radiation Dose	X	X	
Electrical Lead Measurements for the RA, RV and LV Leads	X		
Reportable Adverse Event/Health Care Utilization	(X)	(X)	(X)
Fluoroscopic Views and Orientation Angles Used	X	X	

(X) if applicable

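### Does the missing stop for abandoned steps in section 6.3 undermine the registry's fluoroscopy and radiation results?

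*Combined protocol and SAP*

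**What the plan says.** Section 4.4.2 makes enrolment depend on an attempt: a subject is in the study "if the subject has provided written Patient Informed Consent and CRT implant or an EP procedure was attempted". Section 8.2 starts safety surveillance at the same point. Unsuccessful procedures are therefore in the registry by design.

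Section 6.3 asks for fluoroscopy time and radiation dose by procedural step and gives a beginning and an end for the named steps. In the CRT group, cannulation of the coronary sinus (CS) runs "From the moment the operator directs the technique to cannulate CS until the outer catheter is stable in CS". The second step is "LV lead placement: From the moment outer catheter is stable in LV until the suture sleeve for LV lead is tied down". In the EP group, the first step is given only by analogy, "Catheter insertion: Similar to CS cannulation for CRT implant"; trans-septal puncture runs "From the moment of introducing trans-septal sheath until the sheath is stably paced in LA and the dilator is removed"; geometry creation and mapping end when the operator judges them complete. One step is closed by effort and not by success: "Ablation: From the beginning of ablation until the last attempt for ablation is made". Each group also has an open item for any other step that used fluoroscopy.

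For all patients, section 6.3 separately records total fluoroscopy time and dose, skin-to-skin time and room time, with adverse events where they apply. Section 12.1 plans descriptive summaries of the study objectives with 95% confidence intervals. It names no step-level summary and no rule for an incomplete step.

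**The concern.** Enrolment is by attempt, but most step clocks stop only on success. A patient whose CS is not cannulated, or whose LV lead is not fixed, is enrolled and yet never reaches the defined stop. If cannulation fails, the LV step does not begin either. A site could leave the field blank, time to abandonment, or enter the exposure under the open item. With up to 65 centers, those practices could differ, and a step mean would then describe successes only or mix definitions.

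Section 4.1 also wants to learn which procedural challenges future tools might address. A failed step is such a challenge, and it is the case for which no step value is defined. The ablation step shows that an attempt-based stop was within the authors' reach.

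**Working it through.** **1. Which stops can an abandoned step reach?**

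| Step in section 6.3 | Stop | Reached if abandoned? |
|---|---|---|
| CRT: CS cannulation | catheter stable in the CS | no |
| CRT: LV lead placement | sleeve tied down | no |
| EP: catheter insertion | by analogy with CS cannulation | no, if the analogy is taken literally |
| EP: trans-septal puncture | sheath stable, dilator out | no |
| EP: geometry and mapping | operator's judgement | operator decides |
| EP: ablation | last attempt | yes |

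Three of the six named steps stop explicitly on success, and a fourth does so by inference. The gap in the text is confirmed.

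**2. Which objectives use a step value?** Setting section 4.1 beside the data in section 6.3:

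- Fluoroscopy time and radiation exposure: total time and total dose, all patients.
- Total procedure time: skin-to-skin time, all patients.
- Peri-procedural events: adverse events at the procedure and before discharge.
- Operator experience against exposure: the one-time survey in section 6.2 with the same totals.
- Procedural challenges and new tools: devices implanted, coronary venous anatomy, tools used at each step, software version, and views and angles. Step times would add detail, but a failed LV placement can be recognised from the devices implanted.

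None of the first four needs a step stop. The fifth is descriptive and has other sources.

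**3. How far could a step mean move?** The protocol gives no figure to reproduce here and no inputs for a bias, so this is an illustration only. Let f be the share of attempts in which the step fails, and k the mean fluoroscopy in a failed step divided by that in a completed one; both are assumptions. If failed steps drop out, the successes-only mean falls short of the all-attempts mean by

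1 − 1/[(1 − f) + f·k].

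| f | k = 0.5 | k = 1.5 | k = 2 | k = 3 |
|---|---|---|---|---|
| 2% | −1.0% | 1.0% | 2.0% | 3.8% |
| 5% | −2.6% | 2.4% | 4.8% | 9.1% |
| 10% | −5.3% | 4.8% | 9.1% | 16.7% |

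For example, f = 5% and k = 2 give 1 − 1/1.05 = 4.8%; f = 5% and k = 0.5 give 1 − 1/0.975 = −2.6%, an overstatement. Long failed attempts and early aborts pull in opposite directions, so the sign is open.

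For scale, the relative 95% half-width of a mean is 1.96·CV/√n. At the minimum group size of 250 (section 12.2), it is 6.2% for an assumed coefficient of variation (CV) of 0.5, 9.3% for 0.75 and 12.4% for 1.0. At 750 CRT patients, the most possible if the EP group has its minimum (1000 − 250), it is 3.6%, 5.4% and 7.2%. In a group of 250, the shift is well inside the half-width when failures are rare and k is near 1, and reaches or passes it at the higher assumed values. In a larger group it does so sooner.

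**4. Would the gap be visible?** Section 12.1 reports n with each summary, so blank step fields show as a shortfall against the group total. Section 10 directs central review at missing and inconsistent data. If the other entries are complete, the total less the recorded steps also leaves the exposure of the step left blank.

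**5. A slip in the same line.** The first CRT step ends with the outer catheter stable in the CS; the second begins with it stable in the LV. The two were evidently meant to meet. This looks clerical and has no bearing on failed steps.

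**The case for a change.** The strongest case for a change is that the step data were asked for deliberately, that section 6.3 presents its text as definitions, and that those definitions do not cover patients whom section 4.4.2 enrols. Section 9.2.2 allows fluoroscopy time, exposure and step times to be entered directly on the case report form, so there may be no other source from which to rebuild a missing step. On-site monitoring is discretionary, and a data query would have no written rule to answer it by. A failed cannulation is still a cannulation, so the open item is not an obvious home for it. A repair would need only a few words and a tick box.

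Most of this stands as description: the rule is incomplete, and sites may differ. It does not show that any stated result would be wrong. The case report forms and the Data Management Plan (section 9.1) are separate documents and may already deal with abandoned steps; that cannot be seen from here. The cost is also more than wording, because an amendment under section 14 goes to ethics committees and authorities for notification or approval where required.

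Neighbouring points do not strengthen the case. Section 4.3 describes CRT patients as implanted with the sponsor's generator; since section 4.4.1 applies the criteria before consent, planned use is the natural reading. In Table 1, the unconditional mark for "Device Session Record" is a schedule convention, and a patient without an LV lead may still receive a generator. The absence of a named analysis set in section 12.1 concerns every outcome and does not arise from the step definitions.

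**Conclusion.** No change to the plan is called for. Section 6.3 leaves the stop of an abandoned step unwritten for both CRT steps, for trans-septal puncture and, by inference, for EP catheter insertion. Total fluoroscopy time, total dose, procedure time and adverse events do not depend on those stops, so the plan followed as written still answers its main objectives.

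The consequence is confined to a step-level breakdown that section 12.1 does not specify. Its size and direction cannot be derived from the protocol; the illustrative percentages rest wholly on assumed failure shares, exposure ratios and CVs. An analyst who presents step means can fill the gap in the ordinary way, by giving n per step, saying how abandoned steps were handled and setting the step figures beside the totals.

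This conclusion assumes that the totals are recorded for every enrolled patient, as section 6.3 requires, and that no main claim will be based on a step mean.

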9.2.2 Recording data

Source documents will be created and maintained by the investigational site team throughout the clinical study.

The data reported on the CRFs will be derived from, and be consistent with, these source documents, and any discrepancies will be explained in writing.

The following data can be recorded directly in the CRFs

- Fluoroscopy time
- Radiation exposure
- Time for steps in the study
- MediGuide™-enabled tools used
- Fluoroscopic views and orientation angles used

The CRFs will be signed and validated by the authorized site personnel.

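### Does the mismatch between the end of CRT step i and the start of step ii in section 6.3 damage the fluoroscopy results?

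*Combined protocol and SAP*

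**What the plan says.** Section 6.3 states that "Definitions for the beginning and ending of procedural steps are also provided" and then lists three CRT steps for which fluoroscopy time and radiation dose are recorded:

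- Step i: "CS cannulation: From the moment the operator directs the technique to cannulate CS until the outer catheter is stable in CS".
- Step ii: "LV lead placement: From the moment outer catheter is stable in LV until the suture sleeve for LV lead is tied down".
- Step iii: "Any other steps that required the usage of fluoroscopy".

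The CRT list also asks for "MediGuide™ tools used at each step of the procedure if applicable". For all patients, section 6.3 separately requires "Total amount of fluoroscopy time and radiation dose" and the skin-to-skin procedure time. Section 9.2.2 includes "Time for steps in the study" among the items that may be entered straight into the case report form (CRF).

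The objectives in section 4.1, most of which are repeated in section 12.2, concern fluoroscopy time and radiation exposure, total procedure time and peri-procedural events. None is stated by step. Section 12.1 plans descriptive summaries with 95% confidence intervals and no hypothesis test.

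**The concern.** The two definitions use the same catheter and the same kind of event, but in different places. Appendix A expands CS as coronary sinus and LV as left ventricle, so the terms are not interchangeable. The text does not say whether LV is a slip for CS or a separate, later landmark.

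If some centres start step ii when step i ends, and others wait for a later moment, the same fluoroscopy would be filed under step ii at one centre and step iii at another. With up to 65 centres, the step-level CRT figures might then not be comparable. The list of tools used at each step and the step times would rest on the same uncertain boundary.

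**Working it through.** There is no figure in the plan to reproduce, because no sample size, test or stated result depends on this definition. The check is to see which quantities change when the boundary moves.

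**Notation.** Let T1 be the moment the catheter is stable in the CS (end of step i), T2 a possible later moment read as stable in the LV, and T3 the tying of the LV lead suture sleeve. Let F(a,b) be the fluoroscopy time or dose between moments a and b. Let S be fluoroscopy in step i, and R all fluoroscopy outside both step i and the span from T1 to T3.

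**Reading A (LV is a slip for CS).**
- Step ii = F(T1,T3)
- Step iii = R

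**Reading B (LV is a later landmark).**
- Step ii = F(T2,T3)
- Step iii = R + F(T1,T2)

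**Comparison.**
- Step i is S under both readings; its end does not depend on step ii.
- Steps ii and iii together: A gives F(T1,T3) + R. B gives F(T2,T3) + F(T1,T2) + R, which is also F(T1,T3) + R. They are identical.
- The total is S + F(T1,T3) + R under both, and it is recorded as its own item rather than built from the steps.
- The only quantity that moves is F(T1,T2), from step ii to step iii.

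If a site filed the interval under neither step, the steps would sum to less than the recorded total by exactly F(T1,T2). That shortfall would be visible. An analyst wanting a split that avoids the boundary can report step i and the total minus step i.

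**Which reading is likelier.** The steps are consecutive and share the catheter and the event. The step ii line uses LV for the lead at both its start and its end, so a repeated abbreviation is an easy slip. The same CRT list asks for coronary venous anatomy, which fits a lead delivered by way of the CS. All of this favours reading A without proving it.

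**Reach.** The definition applies only to CRT patients who get as far as step ii. Enrolment requires consent and only that "CRT implant or an EP procedure was attempted", so their number is at most CRT enrolment. That is 250 at the minimum and 1000 − 250 = 750 at the maximum, once the EP minimum is met. These figures are ceilings on records to which the definition applies, not counts of misfiled records. The EP group is untouched: its first step refers back to CRT step i, not step ii.

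**Analyses affected.** Total fluoroscopy time and dose: none. Skin-to-skin time: none. Event rates: none. Section 12 names no step-level summary.

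**The case for a change.** The strongest argument for acting is that the literal wording is what every centre receives, and the error might be hard to undo. Section 9.2.2 allows fluoroscopy time, exposure and step times to go directly into the CRF, so there may be no other source from which to re-split the steps. Section 10.0 relies on central review for missing, inconsistent or outlying data, with on-site visits discretionary, and a plausible split under either reading need not raise a flag. Section 4.1 also lists procedural challenges and new tools among its further aims, which step-level data could serve.

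Part of this stands. The two lines do disagree, and section 6.3 alone does not settle the start of step ii. Anyone who later reports a stand-alone fluoroscopy figure for CRT step ii should state the starting point used.

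The rest is conjecture. No document names a step-level analysis for the further aims. The tool list would change only if a tool were used in the disputed interval and nowhere else in the step. Section 6.2 requires study staff to be qualified for their tasks, which makes divergent readings less likely. The CRF instructions were not available and the flow chart is not shown; either may already fix the point.

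**Conclusion.** The mismatch is real and in the current text, but it is best regarded as a clerical slip that leaves no stated result at risk. The effect on total fluoroscopy time and dose, procedure time, event rates and every analysis named in section 12 is nil, and this holds whichever reading is right. What remains is a possible transfer between steps ii and iii in CRT patients who reach step ii. Its size cannot be estimated, because the documents give neither the length of the interval nor any sign that centres read the line differently.

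No change to the plan follows. Changing the line would alter no planned estimate or conclusion. If a site asks, section 14.0 already allows a written clarification to investigators.

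The conclusion rests on two points: the total is recorded independently of the steps, as section 6.3 requires, and no step-level CRT result is promoted to a study objective.

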6.4 Scheduled Follow-ups

6.4.1 Pre-discharge

During the pre-discharge, adverse events will be reported if applicable.

6.5 Description of activities performed by Sponsor Representatives

Trained sponsor personnel may perform certain activities to ensure compliance to the clinical investigational plan and may provide technical expertise.

6.6 Subject study completion

Patient participation in the study is complete upon completion of pre-discharge visit. When the subject's participation in the clinical study has been completed the subject will return to the medical care as per physician's recommendation.

6.7 Any Known or Foreseeable Factors that May Compromise the Outcome of the Clinical Study or the Interpretation of the Results

All foreseeable factors that may compromise the outcome have been taken into account by clinical study design and well defined subject selection criteria.

6.8 Criteria and Procedures for Subject Withdrawal or Discontinuation

Subjects must be informed about their right to withdraw from the study at any time and for any reason without sanction, penalty or loss of benefits to which the subject is otherwise entitled and withdrawal from the study will not jeopardize their future medical care or relationship with the investigator. Subjects will be asked to specify the reason for the termination but have the right not to answer.

The investigator may decide to withdraw a subject from the study at any time with reasonable rationale. The subject's future care will not be influenced by a decision, voluntary or otherwise, to withdraw from the study. All reasonable efforts should be made to retain the subject in the clinical study until completion of the study.

Reasons for subject's withdrawal include, but are not limited to:

- Subject refuses to continue participating in the study
- Subject does not meet the inclusion/exclusion criteria and does not require additional follow-up for safety reasons.
- Subject is deceased (cause must be documented)
- Subject's non-compliance
- Subject's participation is terminated by the PI or investigator, although the subject consented, since participation is no longer medically appropriate
- Subject is 'lost to follow up': Subject does not adhere to the scheduled follow up visits but has not explicitly requested to be withdrawn from the clinical study. (This does not apply to missed visits). Site personnel should at all times make all reasonable efforts to locate and communicate with the subject in order to achieve subject compliance to the scheduled follow up visits:
 1. A subject will be considered 'Lost to Follow Up' after a minimum of 2 phone calls of a physician or delegate at the investigational site to the subject or contact. These 2 phone calls need to be documented in the subject's hospital records.
 2. If these attempts are unsuccessful, a letter should be sent to the subject's last known address or general practitioner (GP) and a copy of this letter should be maintained in the subject's hospital records.

If a subject withdraws from the clinical study, the site will record the subject's reasons for withdrawal, on a Withdrawal CRF.

When subject withdrawal from the clinical study is due to an adverse event the subject will be followed until resolution of that adverse event or determination that the subject's condition is stable. The status of the subject's condition should be documented at the time of withdrawal.

7.0 COMPLIANCE TO CIP

7.1 Statements of Compliance

The study will be performed in accordance with the most current versions of the World Medical Association (WMA) Declaration of Helsinki, ISO14155 and any regional and/or national regulations and will be compliant to this International Standard and any regional and national regulations, as appropriate.

The investigator will not start enrolling subjects or requesting informed consent from any subject prior to obtaining IRB/EC approval and Competent Authority approval, if applicable, and authorization from the sponsor in writing for the study.

In case additional requirements are imposed by the IRB/EC or Competent Authority, those requirements will be followed, if appropriate. If any action is taken by an IRB/EC, and regulatory requirements with respect to the study, that information will be forwarded to SJM.

As sponsor, SJM has taken up general liability insurance in accordance with the requirements of the applicable local laws. Appropriate country representative will be utilized to understand the requirements for the type of insurance that will be provided for subjects, and such information will be incorporated into the informed consent, as applicable

If required, additional subject coverage or a study specific insurance will be provided by the Sponsor as well.

